12.1.2 Secondary endpoints

We will report OS, EFS, cumulative incidence of cancer and treatment-related mortality.

12.2 Analysis Populations

We will report outcomes on all patients who begin the preparative protocol (corresponding to the intent-to-treat principle) as the primary analysis, and also on those who actually receive transplant and those who successfully engraft (subset analyses).

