To apply this novel non-myeloablative regimen of TLI and ATG for allogeneic HSCT, a clinical trial has been conducted in patients with hematological malignancies other than myelodysplasia or myeloproliferative disorders since December 2001. Analysis of the first 37 patients (last patient enrolled in 2004), 19 of whom had NHL, appeared in the New England Journal of Medicine (39). The regimen consisted of 800 cGy in 10 fractions over 11 days with ATG administered at 1.5 mg/kg/d from day -11 to -7. The median age was 56 (28-65) years and 35% had failed prior autologous HSCT. Multi-lineage chimerism was achieved within 56 days and sustained in 31 of 37 patients. Of the 6 who lost their grafts, 4 were in the setting of progressive disease. Minimal neutropenia was observed and more than half of patients did not require hospitalization. Remarkably and in agreement with the preclinical studies, 35 of 37 patients developed no acute GVHD. Among the 18 patients in partial remission at transplant, 10 achieved complete remission, strongly suggestive of retained graft versus tumor effect. Among the 17 patients in complete remission at transplant, 11 continued to be disease-free at 1.5 years. Transplant-related mortality in this study was just 5% at 180 days. To date, 4 deaths due to disease progression and 4 deaths related to the procedure have been recorded. Overall, these results indicate that preparation with TLI/ATG and allogeneic HSCT is well tolerated, associated with prompt multi-lineage engraftment and a markedly low incidence of acute GVHD, with a strong suggestion of retained graft versus tumor effect.

Update on experience in B cell lymphoma patients

Since the initial report, we continue to accumulate the experience using this novel non-myeloablative preparative regimen. To date, we have performed allogeneic HSCT using TLI/ATG preparative regimen in 111 patients. Sixty four of the patients had malignant lymphoma. The majority of the patients (83%) achieved full donor chimerism (> 95% donor cells) and the transplant was well tolerated.

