The one-year non-relapse mortality was 2% for patients receiving HLA-matched sibling donor graft and 8% for patients having HLA-matched unrelated donor graft. Acute GVHD only occurred in 4% of the patients, while the incidence of chronic GVHD is estimated to be around 35-45% at 2 years. For patients with lymphoma, the disease control was significantly better in patients who responded to salvage chemotherapy prior to transplantation than those who had refractory disease (Figure 4). One possibility is that graft-versus-lymphoma effect is a slow process after non-myeloablative allogeneic transplant and is unable to control high tumor burden or fast growing tumor in time. Therefore, we propose in this project to use non-myeloablative allogeneic HSCT in MF/SS patients after they achieve some degree of disease control with salvage therapy. One important observation was that patients who failed to achieve full donor chimerism had significant chance to relapse after transplant.

[figure not shown]

Figure 4 Actuarial event-free survival among patients with lymphoid malignancies (non-skin) stratified by disease status at transplant (N=64).

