10.1.6 Progression-Free Survival (or other parameters)

Event-free survival (EFS) is the time measurement between the day of allogeneic transplant and the first documented recurrence or death from any cause. Overall survival (OS) is the time measurement between the day of allogeneic transplant and death from any cause.

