12.1 Endpoints

12.1.1 Primary endpoint

The primary efficacy endpoint is PFS at 180 days (defined above). The safety endpoints include GVHD and other treatment related events, including mortality.

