12.3.2 Evaluation of Efficacy

Efficacy will be evaluated by calculating the Kaplan-Meier estimates of progression-free survival (PFS, i.e., probability of remaining alive and free of progression). We will also calculate the cumulative incidence estimate of the progression rate, using non-relapse mortality as a competing risk.

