12.3.3 Methods for handling missing data and non-adherence to protocol

We do not expect to have missing data on key outcome variables, and non-adherence to protocol presumably is limited to failure to complete the entire process of preparation and transplant; this will be handled by subgroup analyses as described.

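### PFS timed from transplant in patients who later engraft is expected to look better than PFS in all patients, even if engraftment has no effect on the lymphoma

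*Combined protocol and SAP*

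**What the plan says.** The primary population is clear: "We will report outcomes on all patients who begin the preparative protocol (corresponding to the intent-to-treat principle) as the primary analysis". Section 12.2 then adds outcomes "and also on those who actually receive transplant and those who successfully engraft (subset analyses". It does not define successful engraftment, give a time window for it, or set a separate time origin for this subset.

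The outcomes include PFS. Section 12.1.1 states: "The primary efficacy endpoint is PFS at 180 days (defined above"; section 12.3.2 states: "Efficacy will be evaluated by calculating the Kaplan-Meier estimates of progression-free survival". The section 12.1.1 cross-reference leads to section 10.1.6, which defines only EFS and OS, both from day 0: "Event-free survival (EFS) is the time measurement between the day of allogeneic transplant and the first documented recurrence or death from any cause".

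Section 4.1.6 schedules peripheral blood chimerism on days +28, +56, +90, +180 and +270 and then yearly. Section 2.4.1 gives a CD3 donor fraction above 95% as the usual meaning of full engraftment and notes that the time to reach it varied widely. Section 2.2 ties graft status to disease outcome in the sponsor's own experience: "Of the 6 who lost their grafts, 4 were in the setting of progressive disease", and "patients who failed to achieve full donor chimerism had significant chance to relapse after transplant".

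Section 12.3.6 names fixed and time-varying proportional hazards models, but for the correlative studies, which it calls exploratory. It does not apply them to the section 12.2 subsets.

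**The concern.** Membership of the engrafted subset is decided after the PFS clock has started. Two things then push its PFS upward.

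- **Guaranteed time.** A patient who dies before engraftment is established is a PFS failure in the full cohort but can never be counted in the subset. The subset is protected from some early failures by construction.
- **Selection linked to outcome.** If graft loss or incomplete chimerism goes with progression, as section 2.2 reports, leaving those patients out removes failures more often than successes.

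The first mechanism works even if engraftment has no influence on the lymphoma. The trial's hypothesis is that a graft-versus-lymphoma effect gives disease control, so a higher PFS curve in engrafted patients is the figure a reader would most readily take as support for it. Section 12.4.2 sets 75% as the target and regards results near 50% as not encouraging, so a shift of several points matters to how the figure is read.

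**Working it through.** **The plan's own figure.** Section 12.4.2 gives 58% to 88%, half-width 15%, for 27/36. The exact (Clopper-Pearson) interval is 57.8% to 87.9%, half-width 15.0%, so the figure reproduces. It is the yardstick below.

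**Inputs.** PFS at 180 days in all patients: 75% (section 12.4.2). Maximum sample size: 40 (section 12.4.1). Early mortality: 5%, an assumption taken from 5% mortality at 100 days in 20 allogeneic cases (section 2.1) and 5% transplant-related mortality at 180 days in 37 patients (section 2.2).

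**Case A: only early deaths are lost.** If a fraction d of patients die before engraftment is established, and other exclusions are unrelated to outcome, subset PFS = PFS / (1 − d).

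- d = 5%: 0.75 / 0.95 = 78.9%, a gain of about 4 points. This places all the early deaths before classification.
- d = 2.5% (half of them): 0.75 / 0.975 = 76.9%, a gain of about 2 points.

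**Case B: patients must also be event-free when classified.** This rule is an assumption. With a constant hazard (also an assumption), the probability of being event-free at day 180, given event-free at day t, is 0.75^(1 − t/180).

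| t | Apparent 180-day PFS | Gain |
|---|---|---|
| Day 28 | 0.75^(0.844) = 78.4% | 3 points |
| Day 56 | 0.75^(0.689) = 82.0% | 7 points |
| Day 90 | 0.75^(0.500) = 86.6% | 12 points |

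**Null check of Case B.** A simulation gave engraftment no effect on the hazard, let 83% of patients be capable of engrafting, and spread engraftment over days 28, 56 and 90. Subset PFS was 79.9% to 82.2%, depending on the mix of times, against 75.0% in all patients. A day-90 landmark removed the false contrast: 86.6% in both groups.

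**Count example.** The earlier series had 6 graft losses in 37 patients, 4 of them with progression. Scaled to 40 patients, 40 × 6/37 = 6.5, taken as 6. Starting from 30/40 and removing 6 patients, of whom 4 failed and 2 did not, gives (30 − 2)/(40 − 6) = 28/34 = 82.4%. This mixes selection with any real graft effect and cannot separate them.

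**Cost of a landmark.** Under the constant hazard, 40 × 0.25 = 10 events are expected by day 180. Before day 90: 40 × (1 − 0.866) = 5.4. Before day 56: 40 × (1 − 0.75^(56/180)) = 40 × 0.086 = 3.4.

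**The case against.** The strongest reply is that little rests on this subset. The primary analysis covers everyone who begins preparation, the engrafted group is labelled a subset, no decision rule uses it, and section 12.3.6 already assigns the relation between chimerism and outcome to time-varying models. All of that stands, and it limits the importance of the point. It does not make PFS from transplant in the subset a sound figure, because section 12.2 plans to report it and nothing carries the section 12.3.6 method across.

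Three stronger readings are tempting and are not supported.

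- A reader might infer that the subset excludes patients because they progressed. No rule says so. Chimerism is tested on fixed days, so a patient who progresses on day 40 can still be classified as engrafted at day +56. Only death before classification guarantees exclusion. In addition, response is first scored at 3 months (sections 4.1.6 and 10.1.1), so a constant hazard from day 0 is a rough model for documented progression. The 82% and 87% figures are therefore illustrations under an added rule.
- A reader might take 28/34 as the gain from selection alone. The earlier series covered other hematological malignancies, section 2.2 gives no 180-day horizon for the losses, and patients who lost a graft may first have counted as engrafted.
- A reader might infer that section 12.3.3 uses the engrafted subset to handle non-adherence, since it says "this will be handled by subgroup analyses as described". That section confines non-adherence to not completing preparation and transplant, which matches the subset of patients actually transplanted. Failure to engraft is not non-adherence.

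**Conclusion.** The point holds for the engrafted-subset analysis only; the primary all-patient analysis and the safety stopping rules are unaffected. The direction is firm: once any death precedes classification, PFS from transplant in this subset is expected to exceed PFS in all patients without any effect of engraftment on disease, and the reported link between graft loss and progression adds to the gap.

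The size is uncertain because section 12.2 does not define engraftment. At the 75% target, the gain is about 4 points if only early deaths are lost (5% assumed, all before classification), and 7 or 12 points if patients must also be event-free to day 56 or day 90 (constant hazard assumed). These compare with the plan's own half-width of 15 points. A definition based on early count recovery would give a smaller gain than one based on sustained or full CD3 chimerism.

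**What to change.** In section 12.2, do not report PFS from transplant in patients selected on later engraftment. Define engraftment as CD3 donor chimerism with a stated threshold, then use one of the following:

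- **Time-varying covariate.** Enter chimerism status as it becomes known, extending the model already named in section 12.3.6 to this analysis.
- **Landmark.** Take patients alive and progression-free at a scheduled chimerism test, group them by chimerism at that date, and time PFS from the landmark. Day +56 keeps more events than day +90. State how the visit window (±5 days in section 4.1.6) is treated.

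Label either result exploratory.

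The change is to wording only, since the chimerism tests are already scheduled. The analytic cost is real. Under a constant hazard, a day +90 landmark drops about 5.4 of 10 expected 180-day events, and day +56 about 3.4. Progression status at day +56 would precede the first scheduled response assessment. The comparison group will also be small: if 83% eventually reach full donor chimerism (section 2.2), about 40 × 0.17 = 7 patients never do, and patients who engraft after the landmark count as not engrafted. With about 10 events, the time-varying model will be imprecise too.

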12.3 Plan of Analysis

12.3.1 Background and Demographic Characteristics

Tabulate summary statistics with measures of variation.

12.3.2 Evaluation of Efficacy

Efficacy will be evaluated by calculating the Kaplan-Meier estimates of progression-free survival (PFS, i.e., probability of remaining alive and free of progression). We will also calculate the cumulative incidence estimate of the progression rate, using non-relapse mortality as a competing risk.

12.3.3 Methods for handling missing data and non-adherence to protocol

We do not expect to have missing data on key outcome variables, and non-adherence to protocol presumably is limited to failure to complete the entire process of preparation and transplant; this will be handled by subgroup analyses as described.

12.3.4 Evaluation of Conduct of trial (including accrual rates, data quality)

Accrual and progress of patients through the regimen will be monitored by the PI, and data quality will be monitored by the BMT data coordinators.

12.3.5 Pharmacokinetics/Pharmacodynamics

N/A

12.3.6 Methods for Correlative Studies

Analyses of the correlation of response and other outcomes with measures of chimerism and other markers will be done with standard methods, including fixed and time-varying Proportional Hazards models and graphical methods. Given the small sample size, we do not expect to have power to do more than explore such correlations.

12.4 Sample Size

12.4.1 Accrual estimates

12-15 patients per year over 3 years for a maximum of 40 patients, subject to stopping rules above.

12.4.2 Sample size justification

The study sample size is based on expected accrual of 12-15 patients per year, up to a maximum of 40 patients over 3 years, with at least 1 year of follow-up in all patients. With 180 day PFS measure and assuming a target rate of 75%, the 95% confidence interval half-width (the precision estimate) will be 15% (e.g., from 58% to 88% if we observe 27/36 PFS). If the PFS is substantially closer to 50%, the results will not be considered encouraging, while if the PFS is even better than 75% the half-width is never greater than 17%.

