12. STATISTICAL CONSIDERATIONS

The primary goal of this study is to provide proof-of-concept evidence for the safety and efficacy of non-myeloablative allogeneic transplant with TLI/ATG conditioning for patients with MF/SS as described above. Safety will be measured at the end of study by rates of GVHD, other measures of side effects, and overall survival (see above for safety monitoring methods). The primary efficacy endpoint is PFS at 180 days. The historical control for safety is the acute GVHD and mortality rates of myeloablative allogeneic treatment. The rationale for this study is based on the expectation that the new non-myeloablative allogeneic transplant will achieve response rates (and subsequent disease control) that is comparable to myeloablative allogeneic transplant, but with a great reduction in GVHD and TRM.

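### Does the lack of a numeric cut-off for an encouraging 180-day PFS result leave the primary efficacy reading open?

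*Combined protocol and SAP*

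**What the plan says.** All places are in the combined protocol and SAP.

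- **Endpoint and analysis.** Section 12.1.1 makes PFS at 180 days the primary efficacy endpoint. Section 12.3.2: "Efficacy will be evaluated by calculating the Kaplan-Meier estimates of progression-free survival". No null rate, significance level or power is given, and section 11.2 rules out an interim efficacy analysis.
- **Size and precision.** Section 12.4.1 expects "12-15 patients per year over 3 years for a maximum of 40 patients". Section 12.4.2 takes 75% as the target rate and gives a 95% interval half-width of 15%, with 58% to 88% for 27/36 as the example.
- **Interpretation.** Section 12.4.2: "If the PFS is substantially closer to 50%, the results will not be considered encouraging". The rest of that sentence is about interval width when PFS exceeds 75%. Section 12.4.3, on criteria for future studies, refers back.
- **Expectation.** Section 12 calls the aim proof of concept and expects that the regimen "will achieve response rates (and subsequent disease control) that is comparable to myeloablative allogeneic transplant", without a figure.
- **Population and clock.** Section 12.2: "We will report outcomes on all patients who begin the preparative protocol". Section 10.1.6, headed as PFS, says: "Event-free survival (EFS) is the time measurement between the day of allogeneic transplant and the first documented recurrence or death from any cause".

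**The concern.** The trial is open, has one arm and has no external response review (section 10.1.7). If the line between a good and a poor efficacy result is not fixed beforehand, it can be drawn once the result is known. The plan gives exact stopping counts for mortality and acute GVHD every five patients, so the adverb used for the primary efficacy endpoint looks thin beside them.

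If every result from 22 to 24 of 36, or 24 to 26 of 40, is treated as unclassified, the open range is wide: it would be hit 36-39% of the time at a true PFS of 60-65%. The exact 95% interval of each of these six results contains both 50% and 75%, so the interval does not supply the label.

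Two further inputs also look loose. Patients who start preparation but are never transplanted have no stated time zero, and no Kaplan-Meier interval method is named. At stake is whether a middling result is described as supporting a further study.

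**Working it through.** **Inputs.** Anchors 50% and 75% (12.4.2). n = 36 is the worked example and equals 12 per year for 3 years; n = 40 is the maximum (12.4.1). Day-180 status is assumed known for everyone, so counts are binomial.

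**1. The plan's own figure.** Exact (Clopper-Pearson) 95% limits for x of n are the 2.5% quantile of Beta(x, n−x+1) and the 97.5% quantile of Beta(x+1, n−x). For 27/36 these are 57.8% and 87.9%, half-width (87.9 − 57.8)/2 = 15.0%. This matches 58% to 88%. Wald gives 60.9-89.1% and Wilson 58.9-86.2%, so the plan used the exact method.

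**2. What the sentence classifies.** The midpoint is (50 + 75)/2 = 62.5%.

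| Result | PFS | Points from 50% | Points from 75% | Reading |
|---|---|---|---|---|
| 21/36 | 58.3% | 8.3 | 16.7 | twice as near to 50%: not encouraging |
| 22/36 | 61.1% | 11.1 | 13.9 | slightly nearer to 50%: unclear |
| 23/36 | 63.9% | 13.9 | 11.1 | nearer to 75% |
| 24/36 | 66.7% | 16.7 | 8.3 | nearer to 75% |
| 23/40 | 57.5% | 7.5 | 17.5 | more than twice as near to 50%: not encouraging |
| 24/40 | 60.0% | 10 | 15 | nearer to 50%, arguably not substantially: unclear |
| 25/40 | 62.5% | 12.5 | 12.5 | equidistant, so not closer to 50% |
| 26/40 | 65.0% | 15 | 10 | nearer to 75% |

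Only 22/36 and 24/40 turn on the adverb.

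**3. How often that count occurs.** P(X = x) = C(n, x) p^x (1−p)^(n−x).

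| True PFS | 22/36 | 24/40 | 22-24 of 36 | 24-26 of 40 |
|---|---|---|---|---|
| 50% | 5.5% | 5.7% | 10.7% | 11.5% |
| 60% | 13.4% | 12.8% | 35.6% | 35.7% |
| 65% | 12.0% | 10.3% | 39.3% | 35.7% |
| 75% | 2.5% | 1.5% | 14.6% | 9.2% |

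The last two columns give the wider range, which includes four results that the sentence cannot call discouraging.

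**4. What the unclear count changes.** The chance of at least x successes at a true 50% / true 75%:

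- n = 36: 12.2% / 97.9% from 22 upward; 6.6% / 95.4% from 23 upward.
- n = 40: 13.4% / 98.8% from 24 upward; 7.7% / 97.4% from 25 upward.

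Either reading separates the two anchors well.

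**5. The intervals.** 22/36 gives 43.5-76.9% and 24/40 gives 43.3-75.1%. Both contain 50% and 75% whichever label is used. That reflects the sample size; a cut-off would not narrow them.

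**6. A stricter rule.** Suppose the one-sided exact 95% lower limit had to exceed 50%. The limit is 48.8% for 23/36 and 49.7% for 25/39 (64.1%), so both would fail although both are nearer to 75%. At n = 36 the count needed rises from 23 to 24. The chance of passing falls from 95.4% to 90.8% at a true 75%, and from 62.9% to 49.3% at a true 65%.

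**7. The side inputs.** Section 12.4.2 plans at least one year of follow-up in all patients and section 12.3.3 expects no missing key outcomes. Day-180 PFS should then be close to a simple proportion, for which the plan's example already uses the exact interval. Each patient who is never transplanted moves the estimate by at most 1/36 = 2.8 or 1/40 = 2.5 points, and section 12.2 already requires that patient to be counted. The stated 17% ceiling for PFS above 75% is true but loose: the maximum there is 14.5% at n = 36 and 13.8% at n = 40, and 17.1% is the value at 18/36. No result depends on it.

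**The case for a change.** The best case for a change is that results nearer to 75% escape the negative label but are never called encouraging. The 75% figure is only a planning value for precision, and the midpoint is not written down. The plan chose to include a criterion and a section on future studies, so the criterion ought to be usable. Where the line falls also matters: at n = 36, moving it from 22 to 24 changes the chance of passing a true 50% rate from 12.2% to 3.3%. A rule would cost a few sentences and no patients.

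The facts in this stand. No section gives a cut-off, and the time origin for patients who are never transplanted is not stated. What does not stand is the step from an unwritten definition to a defect in the plan. The 12.2% to 3.3% contrast moves the line across 23/36, which is nearer to 75% and so cannot be called discouraging on the plan's wording. A limit that must exceed 50% makes that figure a null rate, which the plan never does. A plain midpoint cut-off fits the text, but it only restates it.

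**Conclusion.** No change is needed. The gap is real but small, and analysts would fill it sensibly. The plan brackets the result between 50% and a 75% target, and only 22/36 or 24/40 is unclear. That count has about a 10-13% chance at a true PFS of 60-65% and 1.5-2.5% at 75%. A reader who sees 61% with an interval of 43.5-76.9% knows as much under either label.

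Nothing operational depends on the label. There is no interim efficacy look, the safety rules stand apart, and the estimate is reported regardless. Fixing the midpoint would record what is implied, and a one-sided test against 50% would trade power for a lower false-positive rate that the design never set out to control. The time origin for patients not transplanted is a clarification with no effect shown. The interval method matters little with near-complete follow-up to day 180.

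This rests on three assumptions: day-180 status is known for nearly everyone, the final count lies between 36 and 40, and a result about twice as near to 50% as to 75% (21/36 or 23/40) counts as substantially closer to 50%.
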